7.8. Other Secondary Efficacy Analyses - Duration Endpoints

7.8.1. Population of Interest

The secondary efficacy analyses will be based on the modified Intent-To-Treat population, unless otherwise specified.

7.8.2. Strategy for Intercurrent (Post-Randomization) Events

A Hybrid strategy will be adopted

7.8.3. Endpoint / Variables

The endpoint points are defined as per the primary (Section 7.1) and secondary (Section 7.2) endpoints. The duration is defined as the longest period between any 2 assessments that the subject remains a responder throughout (missing assessments are not considered).

7.8.4. Subgroup, Supportive and Sensitivity Analyses

There are no planned subgroup, supportive or sensitivity analyses for other secondary endpoints.

7.8.5. Statistical Methodology Specification for Duration Endpoints

| |
|--|
| Endpoints |
| 
 Duration of disease control, defined as SLEDAI-2K score ≤ 2 (PI), achieved without treatment failure or study withdrawal [T12.29]. Duration of clinical remission, defined as Clinical SLEDAI-2K score =0 (PI) (Section 15.6.3), achieved without treatment failure or study withdrawal and with corticosteroids at a prednisone equivalent dose of 0 mg/day. [T22.25]. |
| Imputation of Missing Data |
| 
Duration endpoints: There will be no imputation of missing data, only observed data will be considered. Duration will be derived based on the date of the assessment as: Date of last visit meeting criteria - Date of first visit meeting criteria +1
 |
| Model Specification |
| 
 Duration endpoints will be analyzed using ANCOVA to evaluate the treatment effect controlling for treatment group, baseline SLEDAI-2K score (≤ 9 vs. ≥ 10), baseline immunosuppressant use (use vs. non-use), and baseline corticosteroid dose (prednisone equivalent ≤ 10 mg/day vs. >10 mg/day). |
| Model Checking & Diagnostics |
| 
 The Kolmogorov-Smirnov D statistic will be used to test the assumption of normality. Residuals will be reviewed to assess the homogeneity of variance assumption. If the model fit is inadequate additional analysis will be conducted. |

Model Results Presentation

The tables will display:

- Baseline: the number of subjects, mean, standard error, standard deviation, median, 25th percentile, 75th percentile, minimum, maximum for each arm
- At each visit:
 - the number subjects, mean, standard error, standard deviation, median, 25th percentile, 75th percentile, minimum, and maximum,
 - LS Mean, and standard error of the LS Mean for each arm at Weeks 52, 64 and 104.
 - the treatment difference and 95% confidence interval (CI) for the comparison of Arm B vs Arm A; and Arm B vs Arm C at Weeks 52, 64 and 104.
 - the p-value for treatment difference for Arm B vs Arm A at Weeks 52, 64 and 104.

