10.1. Biomarker Change and Percent Change from Baseline Analyses

| |
|---|
| Endpoints |
| The change from baseline and percent change (not for % endpoints) from baseline will be evaluated by visit for each of the biomarkers listed in Table 4 [T15.01-15.02, T15.04-T15.07, T15.09-T15.12, T15.14-T15.15, T25.01-25.02, T25.04-T25.07, T25.09-T25.12, T25.14-T25.15,]. Tables of descriptive statistics for changes in Year 2 relative to at the end of Year 1 will be summarised for immunoglobulins, auto-antibodies and B-Cells [T25.21, T25.22, T25.23]. |
| Population of Interest |
| The Intent-to-Treat population will be used for the analysis. |
| Intercurrent Event Strategy |
| The Year 1 analyses will be performed on the observed data up to IP discontinuation. No imputation will be done for missing data. The Year 1&2 analyses will be performed on the observed data for subjects who completed Week 52 on treatment (Ongoing and on treatment at Week 52 analysis as defined in Section 7.1.5). No imputation will be performed for missing data (data post re-start Belimumab will not be considered). |
| Model Specification |
| Immunoglobulins and Complement An ANCOVA will be used to evaluate the treatment effect controlling for treatment group, baseline SLEDAI-2K score (≤ 9 vs. ≥ 10), baseline immunosuppressant use (use vs. non-use), baseline corticosteroid dose (prednisone equivalent ≤ 10 mg/day vs. > 10 mg/day), and baseline value (continuous). If the distribution of the observed data is not consistent with conducting ANCOVA then a non-parametric rank ANCOVA will also be conducted. Auto-Antibody, B-Cells, T-Cells, and BLYS (Total and Free): A Rank ANCOVA will be used to evaluate the treatment effect controlling for treatment group, baseline SLEDAI-2K score (≤ 9 vs. ≥ 10), baseline immunosuppressant use (use vs. non-use), baseline corticosteroid dose (prednisone equivalent ≤ 10 mg/day vs. > 10 mg/day), and rank baseline value (continuous). |
| Model Checking & Diagnostics |
| For the ANCOVA analysis the Kolmogorov-Smirnov D statistic will be used to test the assumption of normality. Residuals will be reviewed to assess the homogeneity of variance assumption. |

Model Results Presentation

The tables will display:

- Baseline: the number subjects, number of subjects, mean, standard error, standard deviation, median, 25th percentile, 75th percentile, minimum, maximum for each arm

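### The duration endpoints give participants who never respond no value, so taken literally the ANCOVA compares the arms among responders only

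*SAP*

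**What the plan says.** SAP Section 7.8 covers duration of disease control and duration of clinical remission, both on the principal investigator's SLEDAI-2K.

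- Definition (7.8.3): "The duration is defined as the longest period between any 2 assessments that the subject remains a responder throughout", with missing assessments not considered.
- Formula (7.8.5): "Date of last visit meeting criteria - Date of first visit meeting criteria +1".
- Missing data (7.8.5): "There will be no imputation of missing data, only observed data will be considered".
- Population (7.8.1): "The secondary efficacy analyses will be based on the modified Intent-To-Treat population, unless otherwise specified".
- Intercurrent events (7.8.2): "A Hybrid strategy will be adopted". Under Section 7.1, Hybrid makes treatment failures and study withdrawals non-responders.
- Model (7.8.5): "Duration endpoints will be analyzed using ANCOVA to evaluate the treatment effect controlling for treatment group" and three dichotomised baseline factors. Outputs are LS means, differences with 95% CI, and a B versus A p-value at Weeks 52, 64 and 104.

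The October 2020 addendum (Section 2.6) corrects the order of the dates for disease control and starts the count at the first post-baseline visit that meets the criteria. Neither it nor Sections 15.6.4 and 15.6.5 gives a duration for someone who never meets them. The July 2021 addendum keeps both durations in the end-of-study set (Tables 22.09 and 22.20), with MITT as the population and Hybrid in the titles.

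**The concern.** The formula needs two dates. A participant with no qualifying visit has neither, so it returns nothing. Because of the +1, its smallest possible value is 1 day, so it cannot return 0. With no imputation, a program written from this text leaves the outcome blank, and an ANCOVA drops blank outcomes.

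The treatment comparison would then be made among people selected by their response after randomisation, which the combination is expected to change. Responders on Arm B may differ in prognosis from the fewer responders on Arm A, and the three baseline factors cannot be relied on to restore comparability. A regimen that adds genuine but shorter responses could look worse than control on duration. The MITT and Hybrid labels would tell a reader that this selection had not happened.

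**Working it through.** **The plan's own figure.** No sample-size or power figure is given for duration. The only response rates are those behind the primary endpoint (protocol Section 10.2): 70 in Arm A, 140 in Arm B, 10% versus 35%, two-sided 5%, power at least 98%. This reproduces: 98.9% by the pooled z formula and 99.0% by exact enumeration of the likelihood ratio test.

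**How many would be analysed if never-responders are blank.** Number = 70 × pA + 140 × pB, where pA and pB are the proportions with at least one qualifying visit by investigator assessment. Target arm sizes are used, with everyone dosed. The documents do not give pA or pB, so a range is shown; only the first row uses documented rates, and those are Week 52 rates by the independent blinded assessor.

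| pA / pB | Arm A | Arm B | Analysed of 210 |
|---|---|---|---|
| 10% / 35% (planning rates) | 7 | 49 | 56 (27%) |
| 20% / 45% (assumed) | 14 | 63 | 77 (37%) |
| 40% / 65% (assumed) | 28 | 91 | 119 (57%) |

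Investigator assessments are more frequent and any post-baseline visit counts, so the true rates may exceed the planning rates. Even in the last row, 43% of participants would be lost.

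**Whether the direction can reverse.** Illustrative assumption: Arm A responders average 200 days. Arm B has the same proportion at 200 days, plus a further 25% of participants at d days.

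- Responders only: (pA × 200 + 0.25 × d) / pB − 200.
- All participants, never-responders at 0: (pA × 200 + 0.25 × d) − pA × 200 = 0.25 × d.

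At 10%/35% and d = 120: (10 × 200 + 25 × 120) / 35 = 142.9, so −57 days among responders. Over all participants: 50 − 20 = +30 days.

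| pA / pB | d | Responders only | All participants |
|---|---|---|---|
| 10% / 35% | 60 | −100 | +15 |
| 10% / 35% | 120 | −57 | +30 |
| 10% / 35% | 180 | −14 | +45 |
| 40% / 65% | 120 | −31 | +30 |

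Under this assumption the signs differ for every d below 200. If the added responses last as long as the others, the responder-only difference is 0, and the gain in response does not appear in it at all.

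**What 0 days does to the ANCOVA.** At the planning rates about 90% of Arm A and 65% of Arm B values would be 0; at 40%/65%, 60% and 35%. Simulation used 70 versus 140 participants and assumed gamma durations with mean 140 days and SD 90 among responders.

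- Equal arms, durations limited to 1–360 days, ever-response 10% to 50%: a t-test rejected 4.8% to 5.1% of the time.
- 10% versus 35% with equal responder durations: responders-only t-test about 5%; all participants with zeros about 92% by t-test and 98% by rank test.

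These runs used two-sample tests without covariates, so they approximate the planned model.

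**The case against.** The strongest reply is that the SAP nowhere says never-responders are excluded. The population is MITT, Hybrid classes failures and withdrawals as non-responders, and the observed-data sentence sits under a heading about missing data. Someone assessed throughout who never responds has observed non-response. Elsewhere the plan names a subset when it means one, as in the biomarker tables for subjects who completed Week 52 on treatment. All of this stands: a reader might infer that exclusion is a written rule, and it is not. But MITT and Hybrid settle who belongs and who is a non-responder; they do not assign a non-responder a number of days. For time to response, Section 7.7.5 does say how those without a sustained response enter the analysis. Section 7.8 does not, and it has no Summary Measure subsection.

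Three other strong readings are not supported:

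- That ANCOVA is invalid once zeros are included. In the simulation the t-test held its level; the rank test's advantage was power.
- That the 10% and 35% rates fix the loss. They are Week 52 primary-endpoint rates by the blinded assessor, and no rate at all is given for clinical remission.
- That the endpoint measures total time in disease control. It is the longest continuous period, and the 200- and 120-day figures are assumptions.

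Section 7.8.5 also promises additional analysis if model fit is inadequate. That could help with many zeros, but residual checks among responders cannot reveal selection, and Section 7.8.4 plans no sensitivity analysis.

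**Conclusion.** The point holds as a gap in specification with a predictable consequence. As written, the derivation leaves an MITT participant who never responds without a duration, and literal programming turns a comparison labelled MITT into one among responders. About 27% of Arms A and B would be analysed if ever-response equals the planning rates, and 37% to 57% across the assumed higher rates. The sign reversal shows what could happen; it does not predict the result.

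The consequence is bounded. These are other secondary endpoints outside the testing hierarchy, reported beside response proportions by visit and time to sustained response. Nominal p-values and confidence intervals are still planned, so the rule should be written down.

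**What to change.** Add to Section 7.8, by addendum:

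1. An MITT participant with no qualifying post-baseline visit under the Hybrid definition has a duration of 0 days.
2. The arms are compared over all MITT participants, keeping the planned mean difference and 95% CI.
3. Because many values will be 0, the p-value comes from a rank-based ANCOVA with treatment and the three baseline factors.
4. Duration among responders is summarised descriptively, without a p-value.

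Section 10.1 already uses the method for biomarkers ("A Rank ANCOVA will be used to evaluate the treatment effect"), but it cannot be copied unchanged. It adjusts for a ranked baseline value, which duration does not have, and its results presentation gives differences and confidence intervals only for the ordinary ANCOVA.

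The cost is a few sentences and slightly more programming; no new data are needed. The endpoint will then mix whether a response occurred with how long it lasted, and with many ties at 0 the rank test will lean towards the former, so the responder summary should sit beside it. The July 2021 addendum already postdates the first database lock, so a rule added now should be dated and reported as set after the Year 1 results; the Year 1 duration table (T12.29) should state how never-responders were handled.

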7.9. Other Secondary Efficacy Analyses Continuous Endpoints

7.9.1. Endpoint / Variables

Change from baseline in SLEDAI-2K (PI) score and change from baseline in Physician Global Assessment (PGA) by visit.

7.9.2. Summary Measure

The difference in mean change from baseline between Arm B (Combination) vs Arm A (Control).

7.9.3. Population of Interest

The secondary efficacy analyses will be based on the modified Intent-To-Treat population, unless otherwise specified.

7.9.4. Strategy for Intercurrent (Post-Randomization) Events

A hypothetical strategy will be used to estimate what the treatment effect would have been had the subjects not withdrawn from the study . Data collected after TF will be used in the analysis.

7.9.5. Subgroup, Supportive and Sensitivity Analyses

There are no planned subgroup, supportive or sensitivity analyses for other secondary endpoints.

7.9.6. Statistical Methodology Specification for Continuous Endpoints

| |
|---|
| Endpoints |
| 
 • Change from baseline in SLEDAI-2K (PI) score by visit.[T12.30, T22.26,F12.07, F22.10]. • Change from baseline in Physician Global Assessment (PGA) by visit [T12.35,T22.29, F12.08, F22.11]. |
| Imputation of Data for Missed Visits and Following Study Withdrawal |
| 
 • A bayesian repeated measures normal model will be fitted to the data collected prior to study withdrawal, using a Markov Chain Monte Carlo approach, adjusting for treatment group, baseline SLEDAI-2K score (≤ 9 vs. ≥ 10), baseline immunosuppressant use (use vs. non-use), and baseline corticosteroid dose (prednisone equivalent ≤ 10 mg/day vs. >10 mg/day). Non-informative priors will be used. • Quasi-independent samples will be drawn from the posterior distributions for the parameters of the multivariate normal distribution for each treatment group and each missingness pattern. • Each sample leads to a separate imputed dataset, in which the missing values are replaced by values drawn randomly from their conditional distribution. This distribution is based on the observed data and the covariates for that subject using the imputation model and the sampled parameter values. • These steps will be repeated at least 1000 times. |
| Imputation of Data Following Partially Missing SLEDAI-2K |
| 
The same imputation approach will be used for subjects with partially completed SLEDAI-2K scores (i.e. some missing items) however imputed values that are below the minimum possible score (determined from the completed items) will be replaced with the known minimum score. Similarly, imputed values that are above the maximum possible score will be replaced with the known maximum score
 
Minimum and maximum possible SLEDAI-2K scores are detailed in Section 15.6.3.
 |
| Model Specification |
| 
 • Each imputed dataset will be analyzed using ANCOVA to evaluate the treatment effect controlling for treatment group, baseline SLEDAI-2K score (≤ 9 vs. ≥ 10), baseline immunosuppressant use (use vs. non-use), and baseline corticosteroid dose (prednisone equivalent ≤ 10 mg/day vs. >10 mg/day). • The resulting treatment differences and their SEs will be combined across imputations using Rubin's rules. • The models for the SLEDAI-2K endpoints will include the baseline (PI) SLEDAI-2K score (continuous) rather than the stratification factor (≤ 9 vs. ≥ 10). • The model for PGA endpoints will also include the baseline PGA score (continuous). |
| Model Checking & Diagnostics |
| 
The Kolmogorov-Smirnov D statistic will be used to test the assumption of normality. Residuals will be reviewed to assess the homogeneity of variance assumption. If the model fit is inadequate additional analysis will be conducted
 |
| Model Results Presentation |
| 
The tables will display:
 |

- Baseline: the number of subjects, mean, standard error, standard deviation, median, 25th percentile, 75th percentile, minimum, maximum for each arm
- At each visit:
 - the number subjects, mean, standard error, standard deviation, median, 25th percentile, 75th percentile, minimum, and maximum
 - LS Mean, and standard error of the LS Mean for each arm at Weeks 52, 64 and 104.
 - the treatment difference and 95% confidence interval (CI) for the comparison of Arm B vs Arm A; and Arm B vs Arm C at Weeks 52, 64 and 104.
 - the p-value for treatment difference for Arm B vs Arm A at Weeks 52, 64 and 104.

For change from baseline endpoints, a plot of LS means +/- SE by visit and treatment group will be provided.

7.10. Other Secondary Efficacy Analyses: SLEDAI-2K Score ≤ 2 (IBA), Without Current Immunosuppressant and Corticosteroids ≤ 5 mg/day

7.10.1. Endpoint / Variables

This is an additional endpoint to that specified in the protocol. The proportion of participants with a state of disease control defined as a SLEDAI-2K score ≤ 2 (IBA), achieved without current immunosuppressants and with current corticosteroids at a prednisone equivalent dose of ≤ 5 mg/day at Week 52. Immunosuppressant use and corticosteroid reduction are key components of the endpoint in the protocol and are included in the synopsis definition without referring to treatment failure. Hence a supportive analysis that considers immunosuppressant use and corticosteroids without other treatment failure criteria will be conducted.

| Disease Control without Treatment Failure |
|--|
| 
Responder:
 
 • SLEDAI-2K score ≤ 2 (IBA); and • Did not withdraw (including LTFU and death) from the study prior to the visit; and • Did not receive a protocol non-allowed immunosuppressant or change in immunosuppressant on the day of the visit or the 55 days prior; and • Did not receive corticosteroids at a prednisone equivalent dose of >5mg/day (7day average) on the day of the visit or the 6 days prior. 
Non-Responder:
 
 • SLEDAI-2K score >2 (IBA); or • withdrew from the study prior to Week 52 (including, LTFU and death); or • Received a protocol non-allowed immunosuppressant or change in immunosuppressant on the day of the visit or the 55 days prior; or |

| |
|--|
| 
 Received corticosteroids at a prednisone equivalent dose of >5mg/day (7day average) on the day of the visit or the 6 days prior. |
| 
The derivation of SLEDAI-2K score is provided in Section 15.6.3 and withdrawal from the study prior to Week 52 in Section 5.9.
 |
| 
Note: Discontinuation of study investigational product (belimumab or rituximab) is NOT a component of this endpoint, subject who discontinue investigational product will only be non-responders if they also meet 1 of the criteria above.
 |

7.10.2. Summary Measure

The odds ratio at Week 52 between Arm B (Combination) vs Arm A (Control).

7.10.3. Population of Interest

The efficacy analyses will be based on the Modified Intent-To-Treat population, unless otherwise specified.

7.10.4. Strategy for Intercurrent (Post-Randomization) Events

The definition of the endpoint includes consideration for the intercurrent events of study withdrawal (including LTFU and death)(as defined in Section 7.1.4). Treatment failure is not a component of the endpoint and is not considered as an intercurrent event. Data from subjects who discontinue IP is included in this secondary endpoint.

7.10.5. Statistical Analyses / Methods

7.10.5.1. Statistical Methodology Specification

| |
|---|
| 
Endpoint / Variables
 
 The proportion of participants with a state of disease control defined as a SLEDAI-2K score ≤2 (IBA), achieved without study withdrawal, without current immunosuppressants, and with current corticosteroids at a prednisone equivalent dose of ≤5mg/day |
| 
Derivation
 
 Derivation of the endpoint for Arms A, B and C is provided in Section 15.6.4 |
| 
Model Specification
 
 Logistic regression model. Terms in the model: 
 Dependent: response (yes/no) Categorical: treatment group, baseline SLEDAI-2K score (≤9 vs. ≥10), baseline immunosuppressant use (use vs. non-use), and baseline corticosteroid dose (prednisone equivalent ≤10 mg/day vs. >10 mg/day). |

| |
|---|
| Model Checking & Diagnostics |
| 
 The model and diagnostics checks proposed for the primary endpoint will be repeated for the other binary secondary endpoints. |
| Model Results Presentation (T12.39) |
| 
 the number, percentage, SE of percentage, and the 95% CI for the percentage of subjects achieving a response by treatment group the odds ratio and 95% confidence interval (CI) for the comparison of Arm B vs Arm A; and Arm B vs Arm C at Week 52. the p-value for the odds ratio the treatment difference for Arm B vs Arm A at Week 52. |

7.11. Additional Efficacy Analyses

A scatter plot will be produced to assess the degree to which the Principal Investigators assessment of SLEDAI-2K differs from that of the Independent Blinded Assessor at Week 52 [F12.10].

This will only include subjects who have both a PI and IBA SLEDAI-2K total score at Week 52. The scatter plot will show the PI SLEDAI-2K total score on the x-axis and IBA SLEDAI-2K total score on the y-axis. No formal statistical testing will be conducted. Different colours (and symbols) will be used for the following groups of subjects:

- Arm A
- Arm B
- Arm C included in MITT population
- Arm C excluded from MITT population

A Bland-Altman plot of the differences between the IBA and PI scores against the mean of the IBA and PI scores will also be produced at Week 52 [F12.11].

If the conclusions of the analysis of the comparison between Arm A and Arm B for disease control differ between SLEDAI-2K score based on the IBA assessment and the PI assessment at Week 52, then additional analysis may be performed. Additional analysis of endpoints at Week 52 will be performed after the Week 52 Statistical Analysis Complete milestone has been met and will be presented in the Week 52 clinical study report. Analysis of endpoints post Week 52 will be performed as part of the Week 104 reporting.

A difference in conclusion will be determined by the study team after reviewing the complete Week 52 SAC outputs. Consideration will be given to the comparison of the magnitude of the odds ratio in the analysis of:

- The proportion of participants with a state of disease control (IBA)
- The proportion of participants with a state of disease control (PI)

with consideration to the related C.I.s and p-values for the comparison between Arms A and B.

The additional analyses will consider some or all of the following endpoints depending on the results by endpoint for the Week 52 reporting:

- Proportion of participants with a state of clinical remission, defined as a Clinical SLEDAI-2K score =0 (IBA) (Section 15.6.3), achieved without treatment failure or study withdrawal and with corticosteroids at a prednisone equivalent dose of 0 mg/day, by visit.
- Proportion of participants with a state of complete remission, defined as SLEDAI-2K score=0 (IBA), achieved without treatment failure or study withdrawal and with corticosteroids at a prednisone equivalent dose of 0 mg/day, sustained for at least 24 weeks.
- Proportion of participants with a state of clinical remission, defined as Clinical SLEDAI-2K score =0 (IBA) (Section 15.6.3), achieved without treatment failure or study withdrawal and with corticosteroids at a prednisone equivalent dose of 0 mg/day, sustained for at least 24 weeks.
- Proportion of participants with a state of complete remission, defined as a SLEDAI-2K score =0 (IBA), achieved without treatment failure or study withdrawal and with corticosteroids at a prednisone equivalent dose of 0 mg/day, by visit
- Proportion of participants with SLEDAI-2K (IBA) organ improvement by visit (TP, Observed)
- Proportion of participants with SLEDAI-2K (IBA) organ worsening by visit (TP, Observed)
- Time to disease control sustained to Week 104, defined as SLEDAI-2K score ≤ 2 (IBA), achieved without treatment failure or study withdrawal.
- Time to clinical remission sustained to Week 104, defined as Clinical SLEDAI-2K score=0 (IBA) (Section 15.6.3), achieved without treatment failure or study withdrawal and with corticosteroids at a prednisone equivalent dose of 0 mg/day.
- Duration of disease control, defined as SLEDAI-2K score ≤ 2 (IBA), achieved without treatment failure or study withdrawal..
- Duration of clinical remission, defined as Clinical SLEDAI-2K score =0 (IBA) (Section 15.6.3), achieved without treatment failure or study withdrawal and with corticosteroids at a prednisone equivalent dose of 0 mg/day.
- Change from baseline in SLEDAI-2K (IBA) score by visit.
- Duration of disease control, defined as SLEDAI-2K score ≤ 2 (IBA), achieved without treatment failure or study withdrawal.
- Duration of clinical remission, defined as Clinical SLEDAI-2K score =0 (IBA) (Section 15.6.3), achieved without treatment failure or study withdrawal and with corticosteroids at a prednisone equivalent dose of 0 mg/day.
- Change from baseline in SLEDAI-2K (IBA) score by visit.
- Proportion of participants that meet the Lupus Low Disease Activity State (LLDAS) response criteria by Visit based on the IBA assessment.

The analysis will be based on the modified Intent-To-Treat population and use the same intercurrent event strategy (Hybrid as used for the primary endpoint (Section 7.1.4). The analysis will be conducted as specified in Section 7.4.4, Section 7.4.5, Section 7.4.6)

Similarly if there is a difference in the conclusions of the analysis of clinical remission based on the IBA and PI assessment at Week 64, or analysis of disease control based on the IBA and PI assessment at Week 104; then additional analyses will be performed shortly after the Week 104 Statistical Analysis Complete milestone has been met and will be presented in the Week 104 clinical study report. The additional post Week 104 SAC analysis will repeat the analysis of the other secondary endpoints but utilising the IBA assessment instead of the PI assessment. The endpoints to be assessed will potentially include all those previously listed in the Section 7.11.

Note that in the event that the Week 52 reporting does not identify a treatment benefit an abridged set of analysis may be conducted at the end of the study (Week 104).

7.12. Additional Analyses to Assess the Impact of the Coronavirus Disease 2019 (COVID-19) Pandemic on the Secondary Efficacy Endpoints

There will not be any prospective additional analyses carried out to assess the impact of the COVID-19 pandemic on the secondary (non-major) endpoints. However, if the additional analysis of the primary endpoint indicates a major impact of the COVID-19 pandemic, then additional post-SAC analyses will be performed on the secondary endpoints after the Week 52 Statistical Analysis Complete milestone has been met and will be presented in the Week 52 clinical study report.

Similarly, if the additional analysis of the key secondary endpoints indicates a major impact of the COVID-19 pandemic, then additional post-SAC analyses will be performed on the other secondary endpoints after the Week 104 Statistical Analysis Complete milestone has been met and will be presented in the Week 104 clinical study report.

